8.5.3. Urinary Tract Infection (UTI)

Analyses to further characterize the AE of preferred term ‘urinary tract infection’ will be undertaken for only TC1.

CONFIDENTIAL

204947

UTI will be summarized by PVR urine volume category of maximum PVR volume in TC1 (as described in 8.5.1.), and by CIC usage in TC1 (for any reason).

Time to onset of first UTI will be summarized and analysed according to “Study Specific Safety Analyses for Time to Event data” in 8.5.2. Listing will also be prepared.

(Time to onset of first UTI) = (The date of onset of first UTI) – (the date of first treatment) + 1

For subjects who initiated CIC prior to UTI, time between the onset of the use of first CIC and (for any reason) the onset of the UTI will be summarized.

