8.2. Adverse Events of Special Interest Analyses

The definition of AEs of special interest and their MedDRA preferred term is described as [11.6.4](#). The number and percentage of subjects experiencing an AE of special interest and the total number of AEs of special interest will be summarized. Listing will also be produced

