(Time to onset of first CIC) = (The date of using CIC first in TC1) – (the date of first treatment) + 1

Listing of CIC data will be produced. This listing will include the following items.

- Site ID, Subject ID, Treatment group, Start date of CIC / End date of CIC, Duration of CIC, Time to onset of first CIC in TC1, Reason for catheterization (urinary retention, elevated PVR or other)

Study Specific Safety Analyses for Time to Event data	
Endpoint(s)	

 ● Time to onset of first CIC (section 8.5.2) ● Time to onset of UTI (section 8.5.3) ● Time to onset of Urinary retention (section 8.5.4) 	
Model Specification	

 ● Cox proportional hazard model will be used for estimating hazard ratio and its 95% confidence interval. This Cox model include treatment and a stratification factor as fixed effect. 	
Model Results Presentation	

 ● The p-values will not be calculated because p-value is not of interest for safety endpoint in this study. ● The hazard ratio to placebo and its 95% confidence interval will be estimated. 	
Censoring	

 ● If the subject withdraws the study prematurely before receiving 2nd treatment, this subject will be regarded as censored at the date of study withdraw. ● If the subject receives 2nd treatment without any event of interest (i.e., first CIC, UTI or Urinary retention) in TC1, this subject will be regarded as censored at the date of receiving 2nd treatment. 	

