11.6.4. Safety

Adverse Events	
AE'S OF Special Interest	
Adverse events of special interest are classified as follows, and how they will be identified are tabulated below:	
• Urinary tract infections	
• Urinary retention	
• Residual urine volume increased	
• Possible Distant Spread of Toxin	
• Hypersensitivity	
• Potential risk of pyelonephritis	

AEs of Special Interest	Preferred Term
Urinary tract infections	Urinary tract infection; Urinary tract infection bacterial; Urinary tract infection pseudomonal;
Urinary retention	Urinary retention
Residual urine volume increased	Residual urine volume increased
Hypersensitivity	Drug eruption; Dermatitis allergic; Angioedema; Stevens-Johnson syndrome; Toxic epidermal necrolysis; Drug hypersensitivity; Hypersensitivity; Anaphylactic reaction; Anaphylactic shock; Anaphylactoid reaction; Anaphylactoid shock;
Potential risk of pyelonephritis	Bacterial pyelonephritis; Pyelonephritis; Pyelonephritis acute;

As for Possible Distant Spread of Toxin, following SOC and PT terms will be used.

System Organ Class	Preferred Term
Cardiac Disorders	Bradycardia
Eye Disorders	Accommodation disorder Diplopia Extraocular muscles paresis Eyelid function disorder

CONFIDENTIAL

204947

	Eyelid ptosis Pupillary reflex impaired Vision blurred
Gastrointestinal Disorders	Constipation Dry mouth Dysphagia Ileus paralytic
Infections and Infestations	Botulism
Musculoskeletal and Connective Tissue Disorders	Muscular weakness
Nervous System Disorders	Bulbar palsy Cranial nerve palsies multiple Cranial nerve paralysis Dysarthria Facial paralysis Facial paresis Hyporeflexia Hypotonia Paralysis Paresis cranial nerve Peripheral paralysis Peripheral nerve palsy Speech disorder Vocal cord paralysis Vocal cord paresis
Renal and Urinary Disorders	Urinary retention [1]
Reproductive System and Breast Disorders	Pelvic floor muscle weakness
Respiratory, Thoracic and Mediastinal Disorders	Aspiration Diaphragmatic paralysis Dysphonia Dyspnoea Pneumonia aspiration Respiratory arrest Respiratory depression Respiratory failure

[1]; Note that since GSK1351880 is injected into the urinary bladder for the treatment of OAB, and urinary retention is considered an expected localized effect, the PT "urinary retention" will not be considered a Possible Distant Spread of Toxin event for this study.

Treatment Relationship	Definition
Treatment-related	Yes, If relationship in study drug-related and/or injection procedure-related is 'Yes' according to below definitions.

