3.145	SP1	Study specific	Number and Percentage of Subjects with PVR urine volume category (Change from Baseline): GTCs			Y
Clean Intermittent Catheterization (CIC)						
3.132.	SPDB	Study specific	Number and Percentage of Subjects with using CIC: TC1		Y	Y
3.133.	SP1	Study specific	Number and Percentage of Subjects with using CIC: GTCs			Y
3.134.	SPDB	Study specific	Number and Percentage of Subjects with using CIC by maximum PVR urine volume category		Y	Y
3.135.	SPDB	Study specific	Summary of Duration of using CIC: TC1		Y	Y
3.136.	SP1	Study specific	Summary of Duration of using CIC: GTCs			Y
3.137.	SPDB	Study specific	Time to onset of first CIC			Y
Urinary Tract Infection (UTI)						
3.138.	SPDB	Study specific	Number and Percentage of Subjects with UTI by CIC status		Y	Y
3.139.	SPDB	Study specific	Number and Percentage of Subjects with UTI by maximum PVR urine volume category		Y	Y
3.140.	SPDB	Study specific	Time to onset of UTI			Y
Urinary Retention						
3.141.	SPDB	Study specific	Summary of Duration of Urinary Retention: TC1		Y	Y
3.142.	SP1	Study specific	Summary of Duration of Urinary Retention: GTCs			Y
3.143.	SPDB	Study specific	Time to onset of Urinary Retention			Y

CONFIDENTIAL

204947

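### SAP 8.5.3 counts one UTI preferred term while the SAP's own special-interest UTI group counts three, so the PVR, CIC and time-to-UTI analyses can miss events that the incidence tables keep

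*SAP*

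**What the plan says.** SAP 8.5.3 is limited to the first treatment cycle (TC1) and to one preferred term, urinary tract infection: "Analyses to further characterize the AE of preferred term". Four outputs rest on it:

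- UTI by residual volume: "UTI will be summarized by PVR urine volume category of maximum PVR volume in TC1", with a parallel split by CIC use (Tables 3.139 and 3.138).
- Time to first UTI, sent to the Cox model in 8.5.2, which gives a hazard ratio to placebo with a 95% confidence interval and no p-value (Table 3.140, "Time to onset of UTI").
- The CIC-to-UTI interval: "For subjects who initiated CIC prior to UTI, time between the onset of the use of first CIC" to UTI onset is summarised. It has no table number of its own in Appendix 10.

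SAP 11.6.4 identifies the special-interest category for urinary tract infections by three preferred terms: "Urinary tract infection; Urinary tract infection bacterial; Urinary tract infection pseudomonal". SAP 8.2 then reports that category: "The number and percentage of subjects experiencing an AE of special interest and the total number of AEs of special interest will be summarized". The tables are 3.66 (first 84 days of TC1), 3.70 (TC1), and 3.75, 3.80, 3.85 and 3.90 for the other periods.

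The April 2018 plan and the July 2018 amendment have the same wording in both places, and the amendment log lists no change to either section.

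**The concern.** Protocol 4.6.1 puts UTI first among the product risks and names raised PVR and the start of CIC as factors that may have contributed. The 8.5.3 outputs are the only planned analyses of those two links, and they give the only planned hazard ratio for UTI. They should rest on the same events that the SAP calls UTI elsewhere.

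As written, one subject can be a UTI case in one table and UTI-free in another, with nothing in the SAP to explain it. The two extra terms are on the sponsor's own list, so the plan foresees that they may occur. Investigators report a diagnosis (Protocol 12.3.4), which is then coded in MedDRA (Protocol 8, SAP 8.1). Culture results will be at hand for many events, and some UTIs will be diagnosed by outside physicians (Protocol 7.4.6.2.2). A reported term that names a bacterial cause could therefore lead to one of the other two preferred terms.

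**Working it through.** **Comparison of definitions.** The plan states no figure to reproduce here, so the check starts with the text.

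| Output | Source | UTI terms counted |
|---|---|---|
| Special-interest incidence, Tables 3.66 and 3.70 | 8.2, 11.6.4 | 3 |
| All-AE tables by preferred term | 8.1 | every term |
| UTI by CIC status, Table 3.138 | 8.5.3 | 1 |
| UTI by maximum PVR, Table 3.139 | 8.5.3 | 1 |
| Time to first UTI, Table 3.140 | 8.5.2, 8.5.3 | 1 |
| CIC-to-UTI interval | 8.5.3 | 1 |

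Counting a single term is not in itself the inconsistency. Urinary retention is one preferred term in 8.5.4 and also one in 11.6.4. Of these two, only UTI differs between the sections.

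**Effect on a subject.** Take a subject whose only UTI in TC1 is coded to the bacterial or pseudomonal term. In Tables 3.138 and 3.139 the subject counts as having no UTI. In the Cox model the subject has no event. The CIC-to-UTI interval omits the subject. If the same subject later has a second UTI coded to the plain term, the subject is counted, but with too late an onset.

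**Possible size.** The documents do not say how many UTIs will be coded to the other two terms, so the following is an illustration.

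Inputs: 120 subjects per arm (Protocol 4.3); UTI in 26.4% on active and 10.1% on placebo (Protocol 4.6.1, pooled overseas studies). Assumption: a share s of UTI subjects is coded only to the other two terms.

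- Expected UTI subjects: 120 × 0.264 = 31.7 and 120 × 0.101 = 12.1, together 43.8.
- Missed in 8.5.3 if s is equal in both arms: 43.8 × s.
- Risk ratio with equal s: 26.4(1 − s) / 10.1(1 − s) = 2.61 for any s.
- Risk ratio if s applies to the active arm only: 26.4(1 − s) / 10.1.

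| s | Missed, equal s | Risk ratio, equal s | Missed, active arm only | Risk ratio, active arm only |
|---|---|---|---|---|
| 0 | 0 | 2.61 | 0 | 2.61 |
| 5% | 2.2 | 2.61 | 1.6 | 2.48 |
| 10% | 4.4 | 2.61 | 3.2 | 2.35 |
| 20% | 8.8 | 2.61 | 6.3 | 2.09 |

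The crude risk ratio is only a rough guide to what would happen to the hazard ratio. The PVR table splits about 44 events over four volume categories and two arms, so a few misplaced subjects could be visible there.

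**The case against.** The strongest reply is that 8.5.3 is supplementary. It says that it characterises one term further, and it names that term openly. Comparative incidence comes from the 8.1 and 8.2 tables, which keep all three terms. That stands. A reader might infer that events leave the main safety analyses, or that the overall UTI rate and the difference between arms would be understated. The documents do not support that reading.

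The second reply is that the loss may be nil. Protocol 7.4.6.2.2 has an event that meets the culture and leukocyturia criteria recorded as urinary tract infection, which points to the plain term. This also stands, and it probably keeps the loss small. A reader might infer that organism-specific terms will be common because a positive culture is required, but nothing in the documents says that investigators will name the organism. The rule does not close the gap: coding follows what is reported, and a UTI diagnosed elsewhere may be worded differently.

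Third, an equal loss in both arms leaves the risk ratio unchanged, and the documents give no reason to expect different coding by arm. That limits the concern for the hazard ratio. It does not cure wrong cell counts in the PVR and CIC tables.

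Finally, if the special-interest tables show a row per preferred term, a reader could reconcile the counts. The table shells are a separate document, so this cannot be confirmed, and reconciling totals would not restore the missing events to Tables 3.138 to 3.140.

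**Conclusion.** Wrong as written, as an internal inconsistency, and minor. SAP 8.5.3 and 11.6.4 define UTI differently without a stated reason, and the 8.5.3 outputs can treat a UTI subject as UTI-free. The effect is confined to Tables 3.138 to 3.140 and the CIC-to-UTI interval. UTI incidence by arm is not affected.

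The size is unknown: 0 to about 9 of about 44 expected UTI subjects for an assumed share of 0 to 20%. This rests on the overseas rates applying to TC1 in this trial and on those rates covering all three terms. The documents establish neither. They also give no basis for any particular share, and zero is possible.

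**What to change.** Before the codes are broken for the interim analysis, in which Tables 3.138 and 3.139 are reported, add one sentence to SAP 8.5.3: UTI means any preferred term in the urinary tract infections group of 11.6.4. Apply it to Tables 3.138, 3.139 and 3.140 and to the CIC-to-UTI interval. If the single term is intended, state the reason in 8.5.3 and show the term in the table titles.

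The 11.6.4 list can stay as it is. Nothing in the documents shows it to be wrong, so widening it to further infection terms is not needed to remove the inconsistency.

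The cost is one sentence and a small programming change. No new data are needed and no efficacy analysis changes. UTI counts in the 8.5.3 tables may rise slightly.

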#### 4.2. Treatment Arms and Duration

This study consists of a Screening phase (within 28 days period before first treatment), a Treatment phase 1 (double-blind treatment phase: 12 to 48 weeks period after first treatment), and a Treatment phase 2 (open-label treatment phase: 12 to 36 weeks period after first treatment). The duration of overall treatment phase is 48 weeks.

Following the Screening phase, patients meeting the eligibility criteria will be randomly assigned by the registration center to one of the 2 treatment arms (either 100 U GSK1358820 or placebo) in a ratio of 1:1. Subsequently, in Treatment phase 1, patients will receive single treatment with the allocated study drug (20 injections each of 0.5 mL) which will be injected into the detrusor of the bladder. At the randomization, patients will be stratified according to the number of urinary urgency incontinence episodes reported prior to initiation of treatment phase 1 (Week 0),  $\leq 9$  or  $\geq 10$  episodes, over the consecutive 3-day diary completed during the screening phase.

Subjects who meet the criteria for re-treatment (referred to the section 5.3 Re-treatment criteria) between 12 to 36 weeks after 1st treatment can enter to Treatment phase 2 to receive re-treatment (GSK1358820 100 U). Patients are permitted to receive re-treatment until up to 36 weeks after 1st treatment and at most 2 times (Note: a minimum of 12 weeks need to be elapsed since previous study treatment). Subjects who did not receive re-treatment will remain in Treatment phase 1 and continue to visit at the scheduled study visits. Patients who complete the evaluation at 48 weeks after 1st treatment are regarded as the patients who complete the study, regardless of whether the subject was re-treated or not.

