#### 4.6.1. Risk Assessment

Potential Risk of Clinical Significance	Summary of Data/Rationale for Risk	Mitigation Strategy
Investigational Product (IP) : GSK1358820		
Urinary tract infections (UTI)	
As the result of integrated data with 1 completed phase 2 study (191622-077), 2 completed pivotal phase3 study (191622-095 and 191622-520) and an interim cut of the long-term extension study (191622-096), the frequency of UTI as an adverse event, which was occurred in 26.4% of patients in the 100 U BOTOX group and 10.1% of patients in the placebo group (refer to IB section 5.2.4.2 Overactive Bladder).
 
The following potential factors that may have facilitated the occurrence of UTI were:
 
 
1) Elevated PVR urine volume post treatment
 
2) Initiation of clean intermittent catheterization for bladder emptying purposes when urinary retention occurred.
 
3) Patients <math>\geq</math> 65 years are more predisposed to development of UTIs overall regardless of any treatment
 
4) Cystoscopy for study drug administration procedure (intradetrusor injection) during study participation.
 
	
Patients with potential risk for these events will be excluded from this study (refer to Protocol section 5.2 exclusion criteria 4, 5, 17 and 26 )
 
Urinalysis, urine culture and sensitivity test will be performed at each visits. If bacterial infection is confirmed, treatment with antibiotics will be administered in the opinion of the investigators/subinvestigators. The patients are not allowed to receive the injection of the investigational product until bacterial infection is negative (refer to Protocol section 7.4.6.2.Urinalysis).
 
Treatment with antibiotics will be administered to prevent bacterial infection before / after the injection of the investigational product (refer to Protocol section 6.1.2.1.Antibiotics)

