11.4.1.2. Study Phases for AE Data and Safety Date except for AE

Treatment State	Definition
Pre-Treatment	AE Start Date $<$ 1st treatment Date
On-Treatment	If AE onset date is on or after treatment start date & on or before treatment stop date. 1st treatment Date \leq AE Start Date \leq Study Treatment Stop Date
Onset Time Since 1st Dose (Days)	If 1st treatment Date $>$ AE Onset Date = AE Onset Date - 1st treatment Date If 1st treatment Date \leq AE Onset Date = AE Onset Date - 1st treatment Date +1 Missing otherwise.
Duration (Days)	AE Resolution Date - AE Onset Date + 1
Treatment Cycle 1 (TC1) \leq 84 days from 1st treatment	1st treatment Date \leq AE Start Date \leq 1st treatment Date +83
Treatment Cycle 1 (TC1)	1st treatment Date \leq AE Start Date (if the subject completes / withdraws without 2nd treatment) \leq Study Exit/Withdraw Date

CONFIDENTIAL

204947

Treatment State	Definition
	or (if the subject take 2nd treatment) < 2nd treatment Date
GSK1358820 Treatment Cycle 1 (GTC1)	For subjects who received GSK1358820 as 1st treatment: 1st treatment Date ≤ AE Start Date (if the subject completes / withdraws without 2nd treatment) ≤ Study Exit/Withdraw Date or (if the subject take 2nd treatment) < 2nd treatment Date For subjects who received placebo as 1st treatment: 2nd treatment Date /Time ≤ AE Start Date / Time (if the subject completes / withdraws without 3rd treatment) ≤ Study Exit/Withdraw Date or (if the subject take 3rd treatment) < 3rd treatment Date
GSK1358820 Treatment Cycle 2 (GTC2)	For subjects who received GSK1358820 as 1st treatment: 2nd treatment Date /Time ≤ AE Start Date / Time (if the subject completes / withdraws without 3rd treatment) ≤ Study Exit/Withdraw Date or (if the subject take 3rd treatment) < 3rd treatment Date For subjects who received placebo as 1st treatment: 3rd treatment Date / Time ≤ AE Start Date / Time ≤ Study Exit/Withdraw Date
GSK1358820 Treatment Cycle 3 (GTC3)	For subjects who received GSK1358820 as 1st treatment: 3rd treatment Date / Time ≤ AE Start Date / Time ≤ Study Exit/Withdraw Date For subjects who received placebo as 1st treatment: Not applicable because 3 rd treatment of GSK1358820 is not allowed for subjects who received placebo as 1st treatment
Overall	For subjects who received GSK1358820 as 1st treatment 1st treatment Date ≤ AE Start Date ≤ Study Exit/Withdraw Date For subjects who received placebo as 1st treatment 2nd treatment Date ≤ AE Start Date ≤ Study Exit/Withdraw Date

NOTES:

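### The two tables relating UTI to catheter use and maximum PVR ignore event order and the variable length of TC1, so they can show an association where there is no effect; a fixed 84-day version would avoid most of this.

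*SAP*

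**What the plan says.** Protocol 4.6.1 names factors that may facilitate UTI. They include raised PVR after treatment and "Initiation of clean intermittent catheterization for bladder emptying purposes when urinary retention occurred".

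SAP (amended) 8.5.3 relates UTI to these two factors. It states "UTI will be summarized by PVR urine volume category of maximum PVR volume in TC1", and in the same sentence adds a summary "by CIC usage in TC1 (for any reason"). The displays are Table 3.138, "Number and Percentage of Subjects with UTI by CIC status", and Table 3.139, "Number and Percentage of Subjects with UTI by maximum PVR urine volume category". Both are planned at interim and final. Appendix 12 confirms that every reason for CIC counts in the UTI tables. None of these places sets a condition on timing.

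One summary in 8.5.3 does respect order: "For subjects who initiated CIC prior to UTI, time between the onset of the use of first CIC" and the UTI is summarised. It covers only subjects whose CIC came first, has no title of its own in the display list, and has no PVR counterpart.

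The length of TC1 varies. Protocol 4.2 describes "a Treatment phase 1 (double-blind treatment phase: 12 to 48 weeks period after first treatment"). SAP 11.4.1.2 closes the cycle early for re-treated subjects: "if the subject take 2nd treatment) < 2nd treatment Date". Protocol 5.3 allows re-treatment only with PVR below 200 mL, a negative dipstick and no UTI symptoms.

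**The concern.** There are two separate problems.

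- **Order.** A subject with a UTI at week 2 and first CIC at week 6 is counted in the CIC row. A PVR peak recorded after the UTI sets that subject's PVR category.
- **Unequal opportunity.** A subject who stays in TC1 for 48 weeks has nine scheduled post-treatment PVR readings; one re-treated at week 12 has three. The longer stay also gives more time for CIC and for UTI. In addition, TC1 length is not independent of the factors studied, because high PVR or a current UTI blocks the re-treatment that would end the cycle.

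These are the only planned tables that set UTI against the two named risk factors, so readers will use them for that question. A spurious gradient could be read as support for the protocol's proposed mechanism.

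**Working it through.** The plan gives no figure for these tables, so there is nothing to reproduce. The check asks what they would show if CIC and PVR had no effect on UTI.

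**Inputs.** UTI 26.4% and urinary retention 7.1% in the active group of the earlier studies (Protocol 4.6.1), used as illustrative TC1 rates, with retention standing in for CIC. TC1 is 12 weeks if re-treated, otherwise 48 weeks (final) or 24 weeks (interim cut-off, SAP 3.1). The share f re-treated at week 12 is not in the documents; 20%, 50% and 80% are assumed.

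**Route A: events continue after week 12.** Hazards are constant, and UTI and CIC are independent given TC1 length, so P(event) = 1 − exp(−λT). Each λ is solved so that f(1 − e^(−12λ)) + (1 − f)(1 − e^(−48λ)) equals the overall rate.

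For f = 50%, λ is 0.01085 per week for UTI and 0.00249 for CIC. UTI is then 12.21% (12 weeks) or 40.59% (48 weeks), and CIC is 2.94% or 11.26%.

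- Both events: 0.5 × 0.1221 × 0.0294 + 0.5 × 0.4059 × 0.1126 = 0.02465.
- UTI with CIC: 0.02465 / 0.071 = 34.7%.
- UTI without CIC: (0.264 − 0.02465) / 0.929 = 25.8%.

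| Re-treated share | UTI with CIC | UTI without CIC | RR | OR |
|---|---|---|---|---|
| 20% | 29.5% | 26.2% | 1.13 | 1.18 |
| 50% | 34.7% | 25.8% | 1.35 | 1.53 |
| 80% | 37.1% | 25.6% | 1.45 | 1.71 |

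At the interim the RR is only 1.05 to 1.10. If all CIC starts by week 12 and re-treatment is unrelated to it, the RR is 1.00 in every case.

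Maximum PVR behaves the same way. With an assumed independent 2% chance per visit of reaching 200 mL, the chance that the maximum does so is 1 − 0.98³ = 5.9% over three visits and 1 − 0.98⁹ = 16.6% over nine.

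**Route B: high PVR delays re-treatment.** All high PVR arises early, in 7.1% of subjects, with no effect on UTI. Overall f = 50%, but only 25% of the high-PVR group is re-treated at week 12. The share in the rest is (0.5 − 0.071 × 0.25) / 0.929 = 51.91%.

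- High PVR: 0.25 × 12.21% + 0.75 × 40.59% = 33.5%.
- Rest: 0.5191 × 12.21% + 0.4809 × 40.59% = 25.9%. RR about 1.3.
- If no high-PVR subject is re-treated at week 12: 40.6% against 25.3%, RR 1.60.

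With f = 20% the two RRs are 1.09 and 1.18. With f = 80%, the extreme corner, they are 1.64 and 2.35.

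**Order.** Among simulated subjects with both events, UTI came first in 52% to 54% under constant hazards, and in 9% to 19% if CIC starts in weeks 0 to 6.

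**Candidate remedies under the same null.**

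- Fixed 12-week window: OR 0.98 to 1.00 in simulation, that is, no artefact.
- CIC as a time-dependent exposure: rate ratio 0.98 to 1.00.
- Counting CIC only if it started by UTI onset, within 12 weeks (assumed 15% UTI, 7.1% CIC, constant hazards): UTI 7.9% against 15.5%, RR 0.51. It is milder if CIC is early: 0.76 for starts in weeks 0 to 6.
- Cutting maximum PVR off at UTI onset (15% UTI, 5% exceedance per visit): 7.3% against 16.1%, RR 0.45.

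The last two fail because they shorten the exposure period for subjects with a UTI but not for those without.

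**The case against.** The strongest reply is that these are descriptive counts with no test and no attribution rule. A reader might infer that the SAP attributes each UTI to the CIC or PVR row it falls in; the text says only that UTI will be summarised. This stands.

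A reader might also infer that a longer TC1 is enough on its own to create an association. It is not. Protocol 4.6.1 expects the PVR rise mainly in the first 12 weeks, which every subject not withdrawn completes, and if that is the whole story Route A gives 1.00. This stands against Route A. It does not dispose of Route B, because the re-treatment criteria tie TC1 length to PVR even when every high reading is early.

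Third, order is partly handled. The interval from CIC to UTI is summarised for CIC-first subjects, and dated listings of PVR, CIC and adverse events allow a case-by-case check. This eases the order problem for CIC. It does not change Table 3.138 and offers no summary for PVR.

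Finally, a reader might infer that the assessment of the drug's UTI risk is compromised. The documents do not support that. Adverse events within 84 days are summarised by arm, and time to UTI is compared by arm with censoring at re-treatment. Neither depends on these two tables.

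**Conclusion.** The point holds as a minor one. As defined, Tables 3.138 and 3.139 can show a CIC–UTI or PVR–UTI association with no true effect, provided that CIC or high PVR continues to arise after week 12 or that high PVR delays re-treatment. The false risk ratio is about 1.1 to 1.6 in most of the settings examined. It is smaller at the interim, larger only if most subjects are re-treated at week 12 while those with high PVR are not, and 1.00 if neither condition holds.

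These sizes are illustrative. They rest on assumed re-treatment shares, constant UTI hazards, a two-point TC1 length, and event rates borrowed from the earlier studies. What does not rest on assumptions is that the tables contain no order condition and no allowance for unequal follow-up.

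**What to change.** Produce Tables 3.138 and 3.139 for the TC1 window of 84 days or less already defined in SAP 11.4.1.2, either as the main version or beside the whole-cycle version. UTI, CIC and PVR should all be restricted to that window. State whether the Week 12 PVR reading counts, since its target is Day 85, and apply the same rule to every subject. Add the number of UTIs that began before first CIC and before the PVR peak, because a fixed window equalises opportunity but does not settle order. Optionally, add CIC and PVR as time-dependent covariates in the UTI Cox model, which now holds only treatment and the stratification factor.

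Do not move subjects between rows by which event came first, and do not cut maximum PVR off at UTI onset, in a crude table.

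The cost is SAP wording, two repeated tables and a date comparison; no new data are needed. The downside is that UTIs after day 84 do not appear in the fixed-window version, which is a reason to keep the whole-cycle tables alongside.
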